6.3 Self-administration of Romiplostim

Romiplostim will initially be administered by the investigator or qualified health care professional at clinic visits. At the investigator's discretion, subjects who have been dosed in the clinic and achieve a platelet count $\geq 50 \times 10^9/L$ without romiplostim dose adjustments for 4 consecutive weeks will be eligible to self-administer romiplostim or have the injection administered by a caregiver.

Those subjects who self-administer their medication, as well as those who are eligible to self-administer but choose not to, will only be required to return to the site for ongoing evaluations (including platelet counts) at designated study visits (performed every 4 weeks), as long as their dose of romiplostim remains stable.

In the event of a change in dose of romiplostim (per the dose adjustment rules in [Table 1](#)), subjects will be required to return to the clinic for 2 consecutive weeks to confirm that the dose adjustment was appropriate. Subjects will need to be on a stable dose and have a platelet count $\geq 50 \times 10^9/L$ for 2 consecutive weeks without romiplostim dose adjustments before resuming self-administration.

Before subjects begin romiplostim self-administration, it is the responsibility of the investigator to ensure that subjects or their caregivers are trained to prepare and administer the injection. Subjects and/or subject's caregivers will receive training and study tools designed to educate the subject on the proper storage, reconstitution, and self-administration of romiplostim. Once subjects or their caregivers have adequately demonstrated their ability to reliably administer the medication, subjects may be allowed to self-inject (or have the injection given by their caregiver) away from the investigational site. The completion of training on self- injection (or training to a caregiver) will be recorded in the subject's source documentation. All training will be monitored.

The site will be required to ensure that subjects are supplied with necessary materials required for self-injecting, including dispensing of the IP. All used vials of romiplostim must be returned to the clinic for drug accountability. Subject diary cards to record the dose, dosing date, and any dosing or storage errors will be provided to subjects.

While subjects are self-injecting, the IP must be provided to subjects every 4 weeks, during the regular clinic visits. Shipping of romiplostim to subjects is prohibited.

Subjects are expected to store romiplostim in a refrigerator and to notify the site personnel if an error in storage or dosing was made.

6.4 Concomitant Therapy

Throughout the study, investigators may prescribe any concomitant medications or treatments deemed necessary to provide adequate supportive care, except for those listed in [Section 6.6](#).

All prescription and non-prescription concomitant medications, used to treat conditions other than ITP, administered at the time of enrollment, ongoing after enrollment, as well as changes in such concomitant medications and any new concomitant medications taken while the subject is on study, will be recorded on the appropriate eCRF through the EOT or the EOS visit, whichever is later.

Concomitant and Rescue Therapy for ITP

Concomitant medications are allowed for subjects enrolled into the study in any situation deemed medically necessary to increase platelet counts. Medications to increase platelet counts starting before enrollment and continuing unchanged (dose and schedule) while on treatment with romiplostim will be defined as concomitant medications for ITP. Rescue medication is defined as any medication or transfusion, other than romiplostim and excluded medications, that is administered after enrollment to the subject with the intent of raising platelet counts or to prevent bleeding and includes concomitant medications for ITP in which the dose and/or schedule is increased. For the purposes of this study, the permitted rescue medications include the following:

- corticosteroids
- platelet transfusions
- IVIG
- azathioprine
- anti-D immunoglobulin
- danazol

Antifibrinolytics can be used at any time during the study and will not be considered rescue medication(s).

Inhaled and/or topical corticosteroids intended to treat non ITP conditions (eg, inhaled steroids for asthma) will not be considered concomitant medications for ITP or rescue

Product: Romiplostim
Protocol Number: 20101221
Date: 15 August 2014

Page 30 of 69

medications and continuing on such medication(s) will not affect the definition of platelet response.

Rescue medication is allowed throughout the duration of the study when platelet counts are $< 20 \times 10^9/L$ and/or when a subject has bleeding or wet purpura. Rescue medication is also allowed in any situation deemed medically necessary by the treating physician to increase platelet counts to treat or prevent bleeding.

Reduction or discontinuation of concomitant or rescue medications for ITP is recommended based on investigator judgment when platelet counts are $\geq 50 \times 10^9/L$.

Rescue medications are not provided by Amgen.

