6.6 Excluded Treatments During Study Period

The following medications are not permitted during this study:

- commercially available romiplostim (Nplate[®])
- other thrombopoietic receptor agonists (eg, eltrombopag, also known as Promacta[®] or Revolade[®])
- any cytotoxic agents or alkylating agents
- Mycophenolate Mofetil
- Rituximab
- rHuTPO
- interferon
- treatments for ITP other than allowed rescue medications
- any other investigational agents that are not approved for commercial use

If a subject requires administration of any of the medications listed above, Amgen should be consulted before administration of the medication when possible. In all cases, Amgen must be informed within 24 hours. Amgen may decide that the subject will be ineligible to receive additional administrations of IP, in which case, the subject should complete the EOT and EOS visits.

Product: Romiplostim
Protocol Number: 20101221
Date: 15 August 2014

Page 31 of 69

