10.2 Sample Size Considerations

The sample size for this study is governed by the number of pediatric ITP subjects who meet the eligibility requirements during enrollment period. It is estimated that approximately 200 subjects will enroll into this study. The percentage of time achieving platelet response in the first 6 months of treatment period for ITP subjects with romiplostim (both adults and pediatric) is estimated at 74%. The standard deviation of percentage of time is estimated between 30% and 36% based on previous Nplate data. Given the sample size of 200 subjects, the half width of the 95% confidence interval (CI) for the percentage of time achieving platelet response is estimated to be between 4% and 5%.

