10.3.2 Analysis of Key Study Endpoints

10.3.2.1 Efficacy Endpoints

The primary endpoint for this study is the percentage of time with platelet response starting from week 2 in the first 6 months of the treatment period. Platelet response is defined as platelet count $\geq 50 \times 10^9/L$ at a scheduled protocol visit. Platelet counts within 4 weeks of a rescue ITP medication will not be deemed as platelet response. The 95% CI will be calculated for the estimated percentage of time.

Summary statistics of platelet counts and responses will be provided at weeks 1 to 8 and then every 4 weeks.

The percentage of time with platelet response starting from week 2 until the EOT period will be summarized with 95% CI.

Product: Romiplostim
Protocol Number: 20101221
Date: 15 August 2014

Page 48 of 69

Missing platelet counts at weeks 12 and 16, and every 4 weeks thereafter will be imputed by using the mean of the 2 closest non-missing platelet counts within ± 1 week before study discontinuation. If still missing after imputation, platelet counts will be considered as non-response.

The proportion of subjects with splenectomy during the study will be summarized for the subjects who entered this study without splenectomy.

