## **4. Study Endpoints and Covariates**

### **4.1 Study Endpoints**

#### **4.2 Primary Endpoint**

The primary endpoint is the percentage of time with a platelet response, defined as a platelet count of  $\geq 50 \times 10^9/L$  without rescue medication use for ITP in the past 4 weeks, starting from Week 2 in the first 6 months of the treatment period.

A rescue-evaluable weekly platelet count is defined as a weekly platelet count without rescue medication use for ITP in the past 4 weeks.

In the first 6 months of treatment period, a monthly platelet response is defined as a the median of rescue-evaluable platelet counts of  $\geq 50 \times 10^9/L$ .

For each subject, the percentage of time with platelet response during the first 6 months is calculated as the number of monthly platelet response divided by the total number of months. If the monthly platelet response is missing, it will be imputed based on the neighboring monthly platelet response status and rescue medication use in the month. If a monthly platelet response is still missing after imputation, it is considered as no response in this month. Subjects who discontinued the treatment early due to lack of

response (non-responder to romiplostim) before completing 6 months of treatment, the month(s) following their discontinuation of treatment till the 6th month will be imputed as having no monthly platelet response.

The primary endpoint is summarized by descriptive statistics (n, mean, standard deviation, median, Q1 [25th percentile], Q3 [75th percentile], minimum, and maximum) of this percentage of time with platelet response averaging across subjects.

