### **10.5 Efficacy Analyses**

The efficacy analysis will be based on the Efficacy Analysis Set, which includes all subjects who receive at least one dose of romiplostim.

Summary statistics of platelet counts and responses will be provided weekly at Week 1 to 8 and then every 4 weeks for all subjects in the efficacy analysis set and by age groups (<6, 6-<12, 12-<18 years). Platelet response is defined as platelet count

---

$\geq 50 \times 10^9/L$ . Platelet counts within 4 weeks after rescue medication use will not be deemed as platelet responses.

The percentage of time with platelet response starting from Week 2 in the first 6 months of the treatment period will be estimated for all treated subjects and by age groups (<6, 6-<12, 12-<18).

The percentage of time with platelet response from Week 2 till the end of the treatment period will be estimated for all treated subjects and by age groups (<6, 6-<12, 12-<18).

The percentage of time with an increase in platelet counts  $\geq 20 \times 10^9/L$  above baseline starting without rescue medication use during past 4 weeks from Week 2 until the end of the treatment period will be estimated for all treated subjects and by age groups (<6, 6 <12, 12-<18).

The proportion of subjects who used rescue medication for ITP during the study will be summarized by preferred terms. Rescue medication is defined as any medication or transfusion, other than romiplostim and excluded medications, that is administered after enrollment to the subject during screening or throughout the treatment period with the intent of raising platelet counts or prevent bleeding and includes concomitant medications for ITP where the dose and/or schedule is increased.

The proportion of subjects who achieved sustained platelet response for 24 weeks or longer will be summarized. A sustained platelet response is defined as a platelet count  $\geq 50 \times 10^9/L$  without the use of any ITP medications.

The proportion of subjects who had a splenectomy during the study will be summarized for the subjects who entered this study without splenectomy.

Number and percentage of subjects who started self-administration of romiplostim during the study will be summarized.

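### Platelet counts raised by a prohibited ITP drug are scored as romiplostim response when romiplostim continues, because the rescue definition leaves those drugs out

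*Protocol*

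**What the plan says.** - **Definition of rescue.** Protocol 6.4: "Rescue medication is defined as any medication or transfusion, other than romiplostim and excluded medications, that is administered after enrollment". SAP 10.5 uses the same carve-out: "Rescue medication is defined as any medication or transfusion, other than romiplostim and excluded medications".
- **What is excluded.** Protocol 6.6 lists other thrombopoietin receptor agonists (eltrombopag is its example), rituximab, mycophenolate, cytotoxic and alkylating agents, rHuTPO, interferon, and any ITP treatment outside the permitted rescue list.
- **What follows if one is given.** Protocol 6.6 foresees that a child may need one and requires the sponsor to be told within 24 hours. After that, "Amgen may decide that the subject will be ineligible to receive additional administrations of IP". Stopping romiplostim is possible but not automatic.
- **How counts are screened.** SAP 4.2: "A rescue-evaluable weekly platelet count is defined as a weekly platelet count without rescue medication use for ITP in the past 4 weeks". Protocol 10.3.2.1: "Platelet counts within 4 weeks of a rescue ITP medication will not be deemed as platelet response". SAP 4.3, 6 and 10.5 screen the same way. No section masks counts after an excluded drug or sets them to non-response.
- **Rescue incidence.** SAP 4.3 counts children who used rescue medication for ITP, so the carve-out applies there too.

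**The concern.** The rescue filter is the only device in the plan that keeps the effect of other ITP treatment out of the platelet endpoints. It masks 4 weeks after a permitted steroid course. It masks nothing after a prohibited thrombopoietin receptor agonist given alongside romiplostim. The eligibility criteria treat the same drugs as confounders: eltrombopag is barred within 4 weeks of enrolment (4.2.12) and rituximab within 8 weeks (4.2.14). The on-study analysis has no counterpart.

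Three results are exposed: the primary endpoint, both percentage-of-time secondary endpoints (at least 50 × 10⁹/L and +20 × 10⁹/L), and the incidence of rescue use. In the secondary endpoints, counts raised by a prohibited drug qualify as rescue-evaluable and can be carried forward into later weeks. A child given a second platelet-raising drug is probably one doing poorly on romiplostim, so the error would turn poor outcomes into good ones. With no control arm, nothing in the design offsets it.

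**Working it through.** **1. Does any other rule catch the case?**
- The per-protocol set (protocol 10.1.2.4, SAP 7.4) requires a dose and eligibility. It does not remove users of excluded drugs.
- Important protocol deviations (SAP 10.3) are summarised and listed. They do not alter scoring.
- SAP 4.2 scores the months after an early stop for non-response as no response, but only if romiplostim stops for that reason. Under Table 1 of the protocol, weekly 1 µg/kg steps from 1 to 10 reach the maximum at about week 10. Four consecutive very low weeks there put non-responder status at about week 13 at the earliest. A second drug that raises counts prevents the criterion from being met.
- SAP 6 ends the treatment period at last dose plus one week. This closes the window for children who stop romiplostim, not for those who continue.

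The gap is therefore co-administration: a prohibited platelet-raising drug given while romiplostim goes on.

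**2. The plan's own precision.** Inputs from protocol 10.2 and SAP 3.2: N = 200, SD 30 to 36 points, 95% confidence.
- SD 30: 1.96 × 30 / √200 = 4.16 points
- SD 36: 1.96 × 36 / √200 = 4.99 points

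This reproduces the stated 4% to 5%, which serves here only as a yardstick.

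**3. Shift in the primary mean.** SAP 4.2 gives each child the number of response months divided by the number of months, taken here as 6. If k of 200 children each have m months scored as response that the corrected rule would score as non-response, the mean moves by 100 × (k/200) × (m/6) points. The documents give no k or m, so the range is an assumption.

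| k of 200 | m = 1 | m = 2 | m = 3 | m = 4 |
|---|---|---|---|---|
| 2 | 0.17 | 0.33 | 0.50 | 0.67 |
| 5 | 0.42 | 0.83 | 1.25 | 1.67 |
| 10 | 0.83 | 1.67 | 2.50 | 3.33 |

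**4. How much use would match the half-width?** Setting the shift equal to the half-width gives k = half-width × 12 / m.
- m = 3: 4.16 × 12 / 3 = 16.6 and 4.99 × 12 / 3 = 20.0, so 17 to 20 children
- m = 4: 4.16 × 12 / 4 = 12.5 and 4.99 × 12 / 4 = 15.0, so 13 to 15 children

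**5. Rescue incidence.** Each child whose only added ITP treatment is a prohibited drug is missed: 100 × 1/200 = 0.5 points per child.

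**The case against.** The strongest reply is that the affected group is small.

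- **Switching.** A reader might infer that any child moved to eltrombopag or rituximab while on study is credited to romiplostim. The documents do not support that. If romiplostim stops, the SAP treatment period closes at last dose plus one week, and a stop for non-response before month 6 is scored as no response to month 6. One loose end remains. SAP 4.2 has no matching rule for stops for other reasons, and protocol 3.1.1 uses a 36-month treatment period that includes time off romiplostim, so the two documents should agree on the window.
- **Non-responders.** Protocol 3.1.2 and 6.2.3 say they should be discontinued, apart from exceptions through the medical monitor. Six permitted rescue options are also available, and counts after those are filtered. This limits how often a prohibited drug would be added, but does not govern the case when it is.
- **Splenectomy.** A reader might extend the point to counts after surgery. Protocol 6.7 stops romiplostim when a splenectomy is performed, so about one week of counts remains, and SAP 4.4 reports on-study splenectomy separately.
- **Visibility.** A reader might infer that such use would leave no trace. The 24-hour notice to the sponsor and the deviation listing give some. Protocol 7.4 and SAP 10.6.6 are less sure: they refer to concomitant or rescue ITP medication, and under 6.4 a newly started prohibited drug is neither.
- **Descriptive study.** No hypothesis is tested, so no error rate is at stake. The estimate is still the study's main product, and interim summaries support regulatory filings.

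**Conclusion.** The gap is real, appears in both documents, and gives a wrong score in a situation that protocol 6.6 foresees. It is confined to children who receive a prohibited platelet-raising drug while romiplostim continues.

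The direction is fixed: the rule can raise the response percentage and lower the rescue incidence, never the reverse. The size is not known. Under the assumed 2 to 10 children with 1 to 4 affected months it is about 0.2 to 3.3 points on the primary mean, below the planned half-width, plus 0.5 points of rescue incidence per child not already counted for a permitted rescue drug. The formula gives the difference between the two scoring rules. Against what romiplostim alone would have achieved it is an upper bound, since some of those months might have been responses anyway.

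A reader might conclude that the primary result would be materially wrong. The documents do not support that: they give no rate of prohibited use, and a shift as large as the half-width needs roughly 13 to 20 children with 3 or 4 affected months each. The point deserves correction before programming, but does not put the study's main conclusion in doubt.

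**What to change.** Change the analysis only; the lists of permitted and prohibited treatments stay as they are.

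1. In SAP 4.2, 4.3, 6 and 10.5, and in protocol 10.3.2.1, score as **non-response** all weeks and months from the start of any platelet-raising treatment listed in protocol 6.6 (other than study romiplostim) until a pre-stated washout after its last dose. ITP drugs continued unchanged from before enrolment remain concomitant under 6.4 and should not trigger the flag.
2. Set the analysis washout at 4 weeks or more, and at 8 weeks or more for rituximab, in line with the protocol's own entry windows.
3. Allow **no last-observation-carried-forward and no neighbour imputation** across these periods. Making the counts merely not rescue-evaluable would let SAP 4.2 or 4.3 refill the gap with an earlier response.
4. Report such use as a separate row included in the rescue ITP medication total.
5. Confirm that the eCRF captures these drugs with start and stop dates.
6. Leave splenectomy out of the rule, or limit it to on-study surgery. Inclusion criterion 4.1.1 admits children regardless of splenectomy status, so a rule covering every count after splenectomy would score all previously splenectomised children as 0%.

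The cost is SAP wording, a matching line in the protocol, and one programming flag. The reported response percentage may fall slightly and the rescue incidence may rise slightly.

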6.5 Product Complaints

A product complaint is any written, electronic or oral communication that alleges deficiencies related to the identity, quality, durability, reliability, safety, effectiveness, or performance of any investigational or non-investigational product(s) or device(s).

Any product complaint(s) associated with an investigational product(s) or non-investigational product(s) or device(s) supplied by Amgen are to be reported according to the instructions provided in the IPIM.

6.6 Excluded Treatments During Study Period

The following medications are not permitted during this study:

- commercially available romiplostim (Nplate[®])
- other thrombopoietic receptor agonists (eg, eltrombopag, also known as Promacta[®] or Revolade[®])
- any cytotoxic agents or alkylating agents
- Mycophenolate Mofetil
- Rituximab
- rHuTPO
- interferon
- treatments for ITP other than allowed rescue medications
- any other investigational agents that are not approved for commercial use

If a subject requires administration of any of the medications listed above, Amgen should be consulted before administration of the medication when possible. In all cases, Amgen must be informed within 24 hours. Amgen may decide that the subject will be ineligible to receive additional administrations of IP, in which case, the subject should complete the EOT and EOS visits.

Product: Romiplostim
Protocol Number: 20101221
Date: 15 August 2014

Page 31 of 69

6.7 Other Treatment Procedures

If treatment with romiplostim is deemed to be ineffective or intolerable, the investigator may decide to perform a splenectomy. If a splenectomy is performed, the subject will discontinue treatment with romiplostim and follow the procedures for the EOT and EOS visits.

7. STUDY PROCEDURES

All subjects and/or their legally acceptable representatives (eg, parents, legal guardian) will sign and date the informed consent form before subjects can undergo any study-specific procedures. If required by the IRB/IEC, the assent of the child also must be obtained in addition to written informed consent. Refer to the Schedule of Assessments ([Table 2](#)) for an outline of the procedures required at each visit. The visit schedule is calculated from day 1 (first administration of romiplostim). All study procedures have a window of ± 1 day. Procedures that are part of routine care and not considered study specific procedures may be used as screening procedures to determine eligibility.

Missed visits or procedures that are not completed must be reported as such in the subject's source documentation, with an explanation of why the procedures were not completed.

Any blood sample collected according to the Schedule of Assessments ([Table 2](#)) can be analyzed for any of the tests outlined in the protocol and for any tests necessary to ensure minimized risks to study subjects. This includes testing to ensure analytical methods produce reliable and valid data throughout the course of the study. This can also include, but is not limited to, investigation of unexpected results, incurred sample reanalysis, and analyses for method transfer and comparability.

If informed consent is provided by the subject, or the subject's legally authorized representative, Amgen may do additional testing on remaining samples (ie, residual and back-up) to investigate and better understand ITP, the dose response and/or prediction of response to romiplostim, characterize antibody response, or characterize aspects of the molecule (eg, metabolites). Results from this analysis will be documented and maintained, but may not be reported as part of this study.

All subjects enrolled will have samples assayed for binding and if positive, neutralizing antibodies.

